3.3 Public Health Impact

Expanding access to Pre-Exposure Prophylaxis (PrEP) could have significant public health impact. It is estimated that even moderate increases in PrEP use could reduce new HIV infections by as much as 48,000 over the next five years. The goal of this project is to investigate the effect of an intervention to expand access by screening patients and initiating PrEP in the non-traditional setting of the Emergency Department.

4.0 SPECIFIC AIMS AND HYPOTHESIS:

Aim 1: Pre-Exposure Prophylaxis Provision in the ED (PrEPPEP) Trial: The target is to identify 80 PrEP eligible patients over a 12 month period who are interested in initiating PrEP. These patients will randomized to either immediate PrEP (iPrEP) initiation in the ED, a 14-day PrEP starter pack at ED discharge and facilitated linkage to comprehensive outpatient care or facilitated linkage to care for PrEP initiation only.

1a. Evaluate the impact of iPrEP and the PrEP "starter pack" on patients agreeing to PrEP initiation. The primary outcome is PrEP usage at 90-days post enrollment. Secondary outcomes include retention in care, STI diagnosis, risk behavior and PrEP adherence at 30, 60 and 90 days.

1b. Collect data on recruitment and attrition rates, as well as means and standard deviations for key measures that will be needed to plan a definitive trial of ED-initiated PrEP.

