5.0 STUDY DESIGN

5.1 Study Timeline

RCTTimeline		Year 1												Year 2											
		1	2	3	4	5	6	7	8	9	10	11	12	13	14	15	16	17	18	19	20	21	22	23	24
Month																									
IRB Submission/Approval																									
Develop SOPs Aim 2: PPED RCT min, clinical, pharmacy,																									

data management, quality assurance)																								
Aim 2: PrEPPEd RCT Recruitment, Enrollment and Follow-up																								
Aim 3: Data analysis																								
Draft abstract and manuscript																								
Present data																								

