12.3. Adequacy of Protection against Risks

12.3.1 Recruitment & Informed Consent

Participants will be recruited from the MSBI Emergency Department during their ED visit. Participants will be recruited during a single 12-month period. The RA will screen all adult patients using the electronic medical record tracking board. The RA will obtain permission from the clinical team to approach the patient. Using a standardized script, the RA will give a brief description of the study and ask for consent to participate. Patients will be given a consent form that outlines the purpose of the study, length of time of the study, describe what is involved, their responsibilities if they take part in the research, information regarding compensation, potential benefits and foreseeable risks where applicable and study contact information. Potential participants will be asked if they would like time to think about the study and review the consent form. If requested, they will be given as much time as needed to review prior to signing the consent form. In addition to consenting to the survey, patients will also give consent to allow investigators to collect clinical and sociodemographic data from the medical record via chart review and electronic data capture.

The following additional steps will be taken for patient's age 13 to 18. In addition to asking the provider for permission to speak with the patient the study staff will approach the patient and ask them if they are interested in participating in a study about sexual health. If the patient is interested, but is with their adult caretaker the study staff will politely ask as the patient and caretaker if the patient can complete the screening instrument in private. If the patient and caretaker agree the caretaker will be asked to leave the room at which point the study staff will explain the study in more detail and ask the patient if they are willing to participate. If the patient would rather have the caretaker present for the screening and enrollment the study staff will ask to speak with the patient briefly in private to explain that the questions being asked are sensitive and include questions pertaining to sexual activity and drug use. If the patient still would like the caretaker present they will be invited back into the room. If the patient does not want the caretaker to be present they will be asked to wait outside the room until screening and enrollment are complete.

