16.0 Recruitment and Retention Plan

Participants will be recruited, enrolled and followed during one 12-month study period the MSBI emergency departments during their ED visit. The RA will screen all adult patients using the electronic medical record tracking board; to maximize the likelihood of identifying eligible patients, RAs will prioritize approaching patients with a chief complaint that suggests PrEP eligibility (e.g. penile or vaginal discharge, drug overdose or withdrawal). A HIPAA waiver will be requested for these screening activities.

The RA will obtain permission from the clinical team to approach the patient. At this point, the research coordinator will approach the patient to provide information about the study, and if the potential participant is interested, verbal consent will be sought for PrEP behavioral eligibility screening. Patients that meet behavioral criteria for PrEP and are interested in participating will sign written informed consent will be obtained. Patients will be given a consent form that outlines the purpose of the study, length of time of the study, describe what is involved, their responsibilities if they take part in the research, information regarding compensation, potential its and foreseeable risks where applicable and study contact information. Potential participants will be informed if they would like time to think about the study and review the consent form. If requested, they will be given as much time as needed to review prior to signing the consent form. Participants will be informed of the

data sharing plan and the protections against identification of individuals associated with it. In addition to consenting to the survey, patients will also give consent to allow investigators to collect clinical and sociodemographic data from the medical record via chart review and electronic data capture.

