To maximize retention we will use a Locator Form to collect the study participants current address, email address, phone numbers and, with consent, private social media information. In order to facilitate linkage and follow-up, we will also collect similar information for friends and family who know how to reach the patient. All follow-up assessments will be conducted at 30, 60, and 90 from PrEP initiation. All follow-up assessments will be conducted by telephone. Patients will be mailed an appointment reminder and receive a phone call a week and a day before their scheduled assessment. Patients who miss one or more than one follow-up assessment will continue in the study so long as it is within 90 days of their enrollment.

We will provide a \$25 cash incentive for all participants to complete their enrollment, 30, 60 and 90-day follow-up assessments.

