17.2 Trial Safety

Events that would preclude a participant from continuing the intervention:

Safety concerns: Guidelines published by the Centers for Disease Control and Prevention (CDC) provide clear guidance for clinicians prescribing emtricitabine/tenofovir disoproxil fumarate or emtricitabine/tenofovir alafenamide for pre-exposure prophylaxis (PrEP). Indications for not starting or stopping PrEP once started would include renal insufficiency (eCrCL of ≤ 60 ml/min), HIV infection, Hepatitis B, pregnancy, signs or symptoms of acute HIV infection, possible HIV exposure within the last 72 hours. Indications for stopping PrEP would be a new HIV or Hepatitis B infection, worsening renal function, intolerable side effects, hypersensitivity reaction, osteopenia or pregnancy. In the group of patients randomized to iPrEP if any these safety concerns arise during the 14 days the patient is taking the PrEP starter pack they will be addressed by the PI and the patient will be withdrawn from the study since they will no longer be considered PrEP eligible.

Participants could also be removed from the study by the investigator if they do not complete any follow-up assessments within 90-days of enrollment.

Managing any medication related issues: In the group of patients randomized to iPrEP medication related side-effects that occur while the patient is taking the 14-day starter pack will be addressed by the PI. After 14-days or linkage to care (whichever occurs first) the treating PrEP provider will manage the patient as clinically indicated. For any medication related emergency we will provide a "study card" with a number to call to speak with a physician and inform patients if they need immediate treatment to go to the closest emergency room. There is no wash-out period. Patients will told to inform their treating provider of any other medications they are taking including any over-the-counter medicines. For those patients who wish to discontinue PrEP, we will recommend a test to determine HIV status at the time of discontinuation. We will also enquire about the reason for PrEP discontinuation, recent medication adherence and reported sexual risk behavior.

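### Section 16.0 leaves the day-90 primary assessment no catch-up time, dates the calls from two different origins, and does not square the 12-month study period with 12 months of recruitment.

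*Combined protocol and SAP*

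**What the plan says.** **Limit on study time.** Under 16.0, participants who miss one or more calls "will continue in the study so long as it is within 90 days of their enrollment". Section 17.2 adds that the investigator may remove participants "if they do not complete any follow-up assessments within 90-days of enrollment". I found no visit window for any call.

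**Time origin.** The same paragraph of 16.0 counts the 30-, 60- and 90-day calls from PrEP initiation, as does 12.2. Sections 9.5, 10.5.1 (Engagement in Treatment Survey) and 12.1.2 (study procedures) count them from enrollment. The primary outcome is dated from enrollment in 2.0 and 4.0 and from the PrEP initiation visit in 7.1. iPrEP participants take their first dose in the ED (9.3). Control participants are to start within 14 days of the ED visit (7.1, 20.0).

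**Calendar.** Section 16.0: "Participants will be recruited, enrolled and followed during one 12-month study period". Section 12.3.1: "Participants will be recruited during a single 12-month period". Section 4.0 sets the target to "identify 80 PrEP eligible patients over a 12 month period". The 24-month grid in 5.1 has one row for "RCT Recruitment, Enrollment and Follow-up", but its month shading is not legible in the copy reviewed.

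**Handling of gaps.** Section 11.1.1 rules out imputation. Section 11.1.2 includes participants up to their last active visit and gives no rule for an unknown day-90 status.

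**The concern.** The primary outcome is a status on day 90, and the participation limit is also day 90. Someone who cannot be reached that day but answers on day 95 has, on the literal wording, left the study. With no imputation, that person becomes a missing primary outcome even though the answer could have been obtained.

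Counting from PrEP initiation would make the limit act differently in the two arms, because only control participants start later than enrollment. A control participant who never starts would have no origin to count from.

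The calendar wording raises a related question: whether people enrolled in the last three months of a 12-month period are followed to day 90 at all.

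This matters for what the pilot is meant to deliver. Aim 1b and 11.1.3 ask for recruitment and attrition rates to plan a definitive trial, and 17.2 names loss to follow-up as the main threat to validity. Attrition produced by a cut-off in the protocol would be carried into those planning figures as if participants had dropped out.

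**Working it through.** **The plan's own figures.** The only related numbers are the powers in 11.1.3 (40 per arm, two-sided pooled Z test, alpha 0.05, control 50%). Exact binomial enumeration of that test reproduces all seven to four decimals, for example 0.8166 for 50% against 80%. The table is not in error. The plan gives no figure for outcomes lost to a cut-off.

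**1. Catch-up time under the 90-day limit** (limit minus due day, from enrollment)

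| Call | iPrEP, or either arm counted from enrollment | Control, counted from a day-14 start |
|---|---|---|
| 30-day | 90 − 30 = 60 days | due 14 + 30 = 44; 46 days |
| 60-day | 90 − 60 = 30 days | due 14 + 60 = 74; 16 days |
| 90-day | 90 − 90 = 0 days | due 14 + 90 = 104; −14 days |

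Only the call carrying the primary outcome runs out of time, and on the initiation origin it does so only in the control arm. The documents do not say how many participants are reached only after day 90, so I put no size on this. For scale, each 5% of 80 is 4 participants.

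**2. The 12-month period**

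Inputs: 80 participants, 40 per arm (11.1.3); 90 days of follow-up (12.1.2); 12 months (4.0, 12.3.1, 16.0). Even accrual is my assumption.

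- Recruit for all 12 months and stop everything at month 12: 80 × 90/365 = 19.7, about 20 of 80 (24.7%), are enrolled too late to reach day 90. About 60 remain, 30 per arm.
- Close enrollment so that all reach day 90 inside the period: 365 − 90 = 275 days, about 9 months. None is lost. The required rate is 80/9 = 8.9 per month instead of 80/12 = 6.7, which is 33% higher.
- Recruit for 12 months and follow the last participant beyond month 12: none is lost, but 16.0 as worded is not met.

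On the initiation origin with a 14-day lag in every control participant, the first case becomes 40 × 90/365 + 40 × 104/365 = 9.9 + 11.4 = 21.3.

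**3. What the worst case would do**

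At 30 per arm, exact power for 50% against 80% is 0.692 (0.8166 at 40). The largest 95% half-width for a difference in proportions, 1.96 × √(2 × 0.25/n), goes from 0.219 at n = 40 to 0.253 at n = 30. In a pilot that states it is underpowered, the precision of the estimates is the more relevant loss.

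**The case against.** A reader might infer that participants reached late or enrolled late will have no primary outcome. The documents do not support that.

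- The sentence in 16.0 keeps people in after a missed call. It does not say that a call on day 92 is refused or its answer discarded.
- Removal under 17.2 is at the investigator's discretion and covers only participants with no completed assessment. It does not touch someone who answered at day 30 or 60.
- Sections 9.5 and 10.5.1 provide for contact with the provider or review of the record, which can be dated to day 90 whenever the call takes place.
- Neither 4.0 nor 12.3.1 clearly commits every one of the 12 months to accrual, so closing enrollment near month 9 could satisfy all three sections. The grid in 5.1 may also show follow-up after month 12.
- Section 21.0 uses index visit and PrEP initiation side by side, so the two origins may have been meant as one.

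Most of this stands, and it makes the losses conditional. It does not remove the gap. The plan does not say that a day-95 answer counts either, which leaves staff and analyst to decide case by case. Section 10.5.1 describes the provider or record check as confirming what the participant reports, so it is not clearly a substitute for a missed call, and the facility form in Appendix 8 asks about alcohol use disorder and has no PrEP item. If index visit and initiation are the same thing, the control arm's later start still makes the word initiation ambiguous there. No section states an enrollment cut-off.

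**Conclusion.** The point holds as a gap in the rules that should be closed before enrollment. Read literally, 16.0 gives the day-90 primary assessment no catch-up time. Its initiation origin conflicts with 9.5, 10.5.1 and 12.1.2 and would put a control participant starting on day 14 at day 104, while iPrEP participants stay inside the limit. The 12-month wording in 16.0 needs reconciling with 4.0 and 12.3.1.

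The calendar effect ranges from 0 to about 20 of 80. The upper end needs both even accrual over 12 months and a hard stop at month 12, and the plan states neither. The effect of the missing window cannot be sized from the documents. The day-104 result assumes the full 14-day lag and the initiation origin.

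It would go too far to say that the plan discards late answers, that a quarter of participants will lack a primary outcome, or that the sample-size figures are wrong. The cost falls mainly on the retention, usage and recruitment estimates that the pilot exists to supply, not on a confirmatory test.

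**What to change.** 1. **Origin.** In 16.0, and wherever calls or outcomes are dated, count from enrollment in both arms. Bring 7.1, 12.1.2, 12.2 and 21.0 into line.
2. **Window.** In 16.0 and 17.2, replace the 90-day limit with a window for the primary assessment that opens on day 90 and closes later, for example on day 120, identical in both arms. It should not open earlier, because a call on day 83 cannot report use on day 90. Ask about PrEP use as of day 90, and date the provider or record check to day 90.
3. **Calendar.** State in 16.0 either an enrollment cut-off or follow-up of the last participant beyond month 12, and match 4.0 and 12.3.1. Compute the recruitment rate over the months open to enrollment.

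**Cost.** Protocol wording, up to 30 days of extra call attempts for participants not reached on day 90, and some recall error about day 90. A last-dose date alone will not settle day-90 use for someone who stopped and restarted, so the question must ask about that day. If follow-up runs past month 12, the study closes later: 12 months plus 120 days is about 16 months, against a 24-month grid in 5.1. If the 12-month total is kept, the window must fit inside it too: 365 − 120 = 245 days, about 8 months, or 80/8 = 10 participants per month.

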17.0 Data Safety Monitoring Plan

17.1 Roles and Responsibilities

To meet the study's ethical responsibility to its patients, results will be monitored during the trial by [name] (PI). There will be no external data and safety monitoring committee for this study. Study outcomes will be tracked and monitored by the PI.

Study staff are required to disclose any financial conflict of interest to our institutional compliance office. Any identified conflicts of interest are indicated to the patient in the study consent form.

17.2 Trial Safety

Events that would preclude a participant from continuing the intervention:

Safety concerns: Guidelines published by the Centers for Disease Control and Prevention (CDC) provide clear guidance for clinicians prescribing emtricitabine/tenofovir disoproxil fumarate or emtricitabine/tenofovir alafenamide for pre-exposure prophylaxis (PrEP). Indications for not starting or stopping PrEP once started would include renal insufficiency (eCrCL of ≤ 60 ml/min), HIV infection, Hepatitis B, pregnancy, signs or symptoms of acute HIV infection, possible HIV exposure within the last 72 hours. Indications for stopping PrEP would be a new HIV or Hepatitis B infection, worsening renal function, intolerable side effects, hypersensitivity reaction, osteopenia or pregnancy. In the group of patients randomized to iPrEP if any these safety concerns arise during the 14 days the patient is taking the PrEP starter pack they will be addressed by the PI and the patient will be withdrawn from the study since they will no longer be considered PrEP eligible.

Participants could also be removed from the study by the investigator if they do not complete any follow-up assessments within 90-days of enrollment.

Managing any medication related issues: In the group of patients randomized to iPrEP medication related side-effects that occur while the patient is taking the 14-day starter pack will be addressed by the PI. After 14-days or linkage to care (whichever occurs first) the treating PrEP provider will manage the patient as clinically indicated. For any medication related emergency we will provide a "study card" with a number to call to speak with a physician and inform patients if they need immediate treatment to go to the closest emergency room. There is no wash-out period. Patients will told to inform their treating provider of any other medications they are taking including any over-the-counter medicines. For those patients who wish to discontinue PrEP, we will recommend a test to determine HIV status at the time of discontinuation. We will also enquire about the reason for PrEP discontinuation, recent medication adherence and reported sexual risk behavior.

Protection against risks: Participants will be told that their involvement is voluntary. All data obtained during this study will be kept strictly confidential. All hard copy information will be kept in a separate private research room, in a cabinet, under lock and key. A password protected and secured database will hold all computer data. Access to the data will only be open to the co-PIs, co-investigators, and the research associates. All researchers will be required to take the CITI Human Subject web-based course or equivalent.

The investigators will make all efforts to minimize the physical and psychological risks to human subjects. In regard to screening for study entry, patients' discovered to have a clinical/laboratory contraindication for PrEP will be informed and educated by the RA regarding the reason for their ineligibility. Clinical/laboratory abnormalities will be addressed using standard ED protocols. Patients with a primary care provider will be referred back to their doctor for further management. For patients without a primary care provider follow-up will depend on the specific exclusion criteria. Patients with decreased eCrCL will be referred to out-patient nephrology. Patients found to have HBsAg+ will be referred to out-patient Hepatology. Patients found to be HIV+ will be immediately linked to care at PKC as per standard ED protocols. Patients found to be pregnant will be referred to out-patient Obstetrics and Gynecology.

Data related risks are described below under privacy protections and data security and confidentiality. It is possible that patients may become anxious when responding to the risk factor questionnaires. RAs will receive extensive training on counseling patients for PrEP and addressing any patient concerns. If the RAs need additional assistance they will reach out to the PI.

Study protocol will be adhered to as indicated and approved by the Mount Sinai Institutional Review Board and compliance offices.

Consent procedure: Consent procedures are described in Section 9.2. Informed consent procedures for all participants or informants, with attention to literacy level of participants.

Privacy protections: All data obtained during this study will be kept strictly confidential. All hard copy information will be kept in a separate private research room, in a cabinet, under lock and key. A password protected and secured database will hold all computer data. Access to the data will only be open to the co-PIs, co-investigators, and the research associates.

Stopping rules: Given that this trial focuses on feasibility and acceptability of an FDA approved medication being used for its intended purpose in its indented population, no stopping rules are in place.

Disclosure of incidental findings: As discussed in protection against risk, patients who screen out for a medical related reason will be informed of the reason for ineligibility by the PI and be provided with out-patient follow-up for further management. Standard mechanism are in place to address the laboratory abnormalities we expect to find during the screening process.

Data security and confidentiality protections: In order to capture the highest quality data, we will use a web-based system with electronic validation. In addition, we will cross-validate the data for complex errors. Study data will be collected and managed using REDCap electronic data capture tools hosted at the Icahn School of Medicine at Mount Sinai.⁷⁵ REDCap (Research Electronic Data Capture) is a secure, web-based application designed to support data capture for research studies, providing 1) an intuitive interface for validated data entry; 2) audit trails for tracking data manipulation and export procedures; 3) automated export procedures for seamless data downloads to common statistical packages; and 4) procedures for importing data from external sources.

All study data will be entered in the electronic data capture (EDC) system. Study personnel requiring access will have their own Login/Password. Access to clinical study information will be based on individuals' roles and responsibilities. All study data will be transmitted over an encrypted SSL (Secure Sockets Layer) connection that requires user authentication. This application is designed to be in full compliance with the International Conference on Harmonization and Good Clinical Practices (ICH-GCP), the FDA's Code of Federal Regulations 21 Part 11 Electronic Record and Electronic Signatures, the FDA's "Guidance: Computerized Systems

Used in Clinical Trials," and the Privacy Rule of the Health Insurance Portability and Accountability Act of 1996 (HIPAA).

Reportable Events:

HIV acquired while the patient is taking PrEP is considered a serious adverse event and reported to the IRB within 24 hours. Any pregnancy occurring while on PrEP will be considered a serious adverse event and reported to the IRB within 24 hours.

Data Management, Analysis, and Quality Assurance:

Sources of information will come from the socio-demographic questionnaires, behavioral risk factor questionnaires, PrEP attitude and knowledge measures, satisfaction questionnaires, laboratory test results, adherence questionnaires, electronic medical records and VSQ-9 study visit questionnaires. As noted above all study data will be entered in the electronic data capture (EDC) system that requires unique user Login/Password.

The greatest threat to study validity is likely to be loss to follow-up. We have attempted to minimize this possibility by requiring detailed locator information and performing facilitated linkage. The follow-up rate in our HCV screening program is 50% where there is no requirement for locator data or facilitated linkage. We expect the rates of follow-up in this program to be closer to 85% as was seen in Project BRIEF where facilitated linkage mechanisms were used. We will also collect short term (30-day) and longer term follow-up (60 & 90-days) data to ensure that, even if there is drop-out at each time point, we will still have usable data for outcome analysis.

Given that the study will examine patients presenting to one urban academic emergency department, the results may not generalize to other EDs. We do not see this as problematic as more widespread dissemination first requires some data on the impact of a PrEP screening, initiation and linkage program in the ED setting. We anticipate that the results from this study will set the foundations for a future multicenter R01 that will specifically address generalizability.

